Arm A (APR-246). Patients will receive a fixed dose of 4.5 g APR-246 (1.5 g of the dose during first 45 minutes followed by 3 g of the dose during 5 hours 15 minutes) on Days 1 to 4, with carboplatin AUC 5 and PLD 30 mg/m² administered concurrently on Day 4 (treatment repeated every 28 days for up to six cycles).

Arm B (Control). Carboplatin AUC 5 and PLD 30 mg/m² administered on Day 1 of each 28-day cycle, repeated for up to six cycles.

Number of patients:

The trial will enroll up to a maximum of 400 patients with positive IHC staining for p53.

Diagnosis and main criteria for inclusion:

Inclusion criteria:

1. Archived sections from the original FFPE sample reviewed by a gynecological pathologist confirming High Grade Serous Ovarian Cancer, High Grade Serous Peritoneal Cancer or Primary Fallopian Tube Cancer, and positive IHC staining for p53 assessed according to defined standard (as detailed in the laboratory manual). Cases that do not show p53 staining will not be included.
2. Radiologically-confirmed Disease Progression between six and twenty-four (6-24) months after a first or second platinum based regimen.
3. At least a single (RECIST v1.1) measurable lesion.
4. Adequate organ function prior to registration:
 - a) Bone Marrow Reserve:
 - Absolute neutrophil count (ANC) $\geq 1.5 \times 10^9/L$,
 - Platelets $\geq 100 \times 10^9/L$,
 - Hemoglobin $\geq 9 \text{ g/dL}$.
 - b) Hepatic:
 - Total bilirubin level $< 1.5 \times \text{ULN}$,
 - ALT and AST $< 2.5 \times \text{ULN}$.
 - c) Renal:
 - Calculated creatinine clearance $> 30 \text{ mL/min}$.
 - d) Electrolytes
 - Potassium within institutional normal ranges.

5. Toxicities from previous cancer therapies, excluding alopecia, must have recovered to grade 1 (defined by CTCAE version 4.0). Chronic stable grade 2 peripheral neuropathy secondary to neurotoxicity from prior therapies may be considered on a case by case basis by the Principal Investigator.
6. If of childbearing potential, negative pre-treatment serum pregnancy test.
7. If of childbearing potential, willing to use an effective form of contraception (see below) during chemotherapy treatment and for at least six months thereafter.
Such methods include: (if using hormonal contraception this method must be supplemented with a barrier method, preferably male condom).
 - Combined (estrogen and progestogen containing) hormonal contraception associated with inhibition of ovulation:
 - Oral
 - Intravaginal
 - Transdermal

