6.5.2 Dose Modifications for Systemic Chemotherapy

For typical hematological (Table 3 and Table 4) and non-hematological (Section 6.5.2.2) adverse events seen with carboplatin and PLD, the dose modifications specified below should be applied. However, if any adverse events occur that are not typical or that are considered unusual, the Sponsor should be consulted prior to re-treating the patient.

If due to adverse events the patient is unable to continue treatment with PLD, the Investigator may consider continuing with carboplatin monotherapy and APR-246 in Arm A to a total of six cycles (including all prior combination chemotherapy cycles).

If due to adverse events the patient is unable to continue chemotherapy with both PLD and carboplatin, the patient may continue monotherapy APR-246 up to 6 courses in total if the following criteria are met:

- There is CA-125 reduction suggestive of treatment benefit (eligible patients)
- Latest radiological scans shows evidence of response
- Patient is evaluated as not having symptoms suggestive of progressive disease
- The Investigator assessment is that APR-246 monotherapy is of continued benefit to the patient
- APR-246 administration has been approved by the Sponsor.

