6.5.3 Hypersensitivity / Adverse Drug Reactions to Chemotherapy Agents

All patients will be carefully monitored for clinical features of hypersensitivity reactions. Should a hypersensitivity reaction to carboplatin occur during infusion, this must be discontinued and an attempt at desensitization may be made subsequently if deemed appropriate by the Investigator in discussion with the patient. The timing of this will be at the discretion of the Investigator depending on the initial dose of carboplatin received.

Desensitization should be performed according to local practices and monitoring.

The desensitization procedure should take place with resuscitation facilities within easy access with regular observations and a trained nurse present throughout administration of APR-246 and chemotherapy. If at any point during the dose escalation allergic signs or symptoms are apparent, the carboplatin infusion must be discontinued.

All subsequent cycles should then be given using this procedure.

If it is not possible for the patient to continue to receive carboplatin due to unmanageable hypersensitivity, the Investigator in consultation with the Sponsor can consider either to remove the patient from the study or change to cisplatin monotherapy. Cisplatin monotherapy will be administered in place of the combination chemotherapy on day 4 of all remaining treatment cycles, up to a maximum of 6 cycles (including prior combination chemotherapy).

The cisplatin monotherapy should be administered, monitored and modified according to the local practices at the investigational site.

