6.7 Contraception

Female patients of childbearing potential (defined as < 2 years after last menstruation and not surgically sterile) and their male partners must use a highly effective method of contraception resulting in a low failure rate (i.e. less than 1% per year) during chemotherapy treatment and for at least six months thereafter. These methods of contraception according to the note for guidance on non-clinical safety studies for the conduct of human trials for pharmaceuticals (CPMP/ICH/286/95, modification) include consistent and correct use of hormone containing implants and injectables, combined oral contraceptives, hormone containing intrauterine devices, barrier methods with spermicide, true sexual abstinence when this is in line with the preferred and usual lifestyle of the patient and partner with vasectomy. Periodic abstinence (e.g., calendar, ovulation, symptothermal, post-ovulation methods), declaration of abstinence for the duration of a trial, and withdrawal are not acceptable methods of contraception. If using hormonal contraception this method must be supplemented with a barrier method, preferably male condom (female condom and male condom should not be used together).

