- **Pharmacokinetics:** Arm A only. On Cycle 1, days 1, 2, and 4; please refer to Section 8.4 for PK sampling time points.
- **Exploratory biomarkers:** Arm A blood samples. Cycle 1 on days 1, 4 and 5. Cycle 2 on days 1, 4 and 5. Cycle 6 on day 1. Arm B blood samples. Cycle 1 and 2 on days 1 and 2. Cycle 6 on day 1. Refer to laboratory manual for detailed instructions.
- **APR-246 administration:** Arm A only on days 1, 2, 3 and 4.
- **Chemotherapy administration (Carboplatin and PLD):** Arm A on day 4. Arm B on day 1.
- **Adverse Events:** All adverse events since the last visit should be recorded. Even though pre-medicated, patients should be closely monitored.
- **Concomitant medications.**

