7.2.5 End of Treatment Visit

This visit should take place 7 days after the completion of 6 cycles of chemotherapy (between day 28 and day 35 of cycle 6) or up to 30 ± 2 days after the last administration of APR-246 if treatment is stopped early for any reasons.

- **Physical examination***: Height, weight, body surface area, and description of external signs of cancer.
- **QoL questionnaires**
- **Tumor Assessment:** CT scan/MRI. If the patient has stopped APR-246 treatment prior to completion of 6 cycles, tumor assessment should be performed at end of treatment visit if not done at the last cycle.
- **ECOG performance status.**
- **Hematology:** Hemoglobin, hematocrit, MCV, platelet count, WBC and WBC differentials.
- **Coagulation:** INR and APTT, if patient is receiving warfarin assessments should be done weekly.
- **Blood chemistry:** Sodium, potassium, calcium, magnesium, chloride, glucose, creatinine, total bilirubin, aspartate transaminase [AST], alanine transaminase [ALT], urea, total protein, albumin and lactic dehydrogenase [LDH], direct bilirubin and uric acid.
- **CA-125.**
- **ECG:** Standard 12-lead ECG.
- **Exploratory biomarkers:** Blood Sample. Refer to laboratory manual for detailed instructions.

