7.4.1 Maternal Exposure

If a patient becomes pregnant during the course of the study investigational product should be discontinued immediately.

Pregnancy itself is not regarded as an adverse event unless there is a suspicion that the investigational product under study may have interfered with the effectiveness of a contraceptive medication. Congenital abnormalities/birth defects and spontaneous miscarriages should be reported and handled as SAEs. Elective abortions without complications should not be handled as AEs. The outcome of a pregnancy should be followed up and documented even if the patient was withdrawn from the study.

If a pregnancy occurs during exposure to investigational product or in the 30 days after discontinuing investigational product, then Investigators or other site personnel must inform the Theradex® Safety Desk immediately, or **no later than 24 hours** of when he or she becomes aware of it.

The same timelines apply when outcome information is available.

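### Contraception is counted from the end of chemotherapy, so an Arm A patient who continues APR-246 alone has no minimum period counted from her last APR-246 dose: about 71 to 155 days remain on schedule, fewer with delays (minor wording fix)

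*Combined protocol and SAP*

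**What the plan says.** Criterion 7, identical in the synopsis and in section 5.1, requires a patient of childbearing potential to be "willing to use an effective form of contraception (see below) during chemotherapy treatment and for at least six months thereafter". Section 6.7 asks for a highly effective method "resulting in a low failure rate (i.e. less than 1% per year) during chemotherapy treatment and for at least six months thereafter". None of the three places names APR-246 or study treatment as a whole.

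Section 6.5.2 provides that a patient who, because of adverse events, is "unable to continue chemotherapy with both PLD and carboplatin, the patient may continue monotherapy APR-246 up to 6 courses in total", subject to five conditions. One is "Latest radiological scans shows evidence of response"; another is sponsor approval. In that sentence chemotherapy has ended while APR-246 goes on. Section 7.2.4 likewise lists APR-246 administration and chemotherapy administration as separate items and identifies chemotherapy as carboplatin and PLD.

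Other windows are anchored differently. Section 7.4.1 requires a report of a pregnancy that "occurs during exposure to investigational product or in the 30 days after discontinuing investigational product", and section 7.3.3.1 collects adverse events until 30 days after the last study treatment of any kind.

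**The concern.** On a route that the protocol expressly permits, the contraception period starts with the wrong drug. The longer a patient stays on APR-246 alone, the less required cover she has after her last dose, and the visible text gives no reason for that.

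The plan takes pregnancy on the investigational product seriously. Section 7.4.1 stops the product at once, and section 5.3 lists pregnancy as a reason to end study treatment. Table 9 schedules a serum pregnancy test at pre-treatment only, so contraception is the main continuing safeguard. What is at stake is participant protection in a small group. No endpoint or analysis depends on it.

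**Working it through.** The plan states no figure here, so there is none to reproduce. The check is date arithmetic.

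**Inputs**
- Cycle length 28 days, at most six cycles; in Arm A, chemotherapy and the last APR-246 dose of a cycle both fall on Day 4 (synopsis, 6.4.1).
- APR-246 alone is allowed up to six courses in total (6.5.2).
- The first on-treatment scan is at the end of cycle 2 (Table 9, 7.2.4). Because 6.5.2 needs a scan showing response, the earliest switch on the planned scans is after cycle 2.
- Six months = 365.25 / 2 = 182.6 days (calendar range 181 to 184).

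**Formula.** Let *k* be the last chemotherapy cycle, *m* the last APR-246 cycle (2 ≤ *k* < *m* ≤ 6), and *D* the total delay in days between those two doses.

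Minimum cover after the last APR-246 dose = 182.6 − 28 × (*m* − *k*) − *D*

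**On schedule (*D* = 0)**

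| Cycles of APR-246 alone (*m* − *k*) | (*k*, *m*) combinations | Minimum cover, days |
|---|---|---|
| 1 | 4 | 182.6 − 28 = 154.6 |
| 2 | 3 | 182.6 − 56 = 126.6 |
| 3 | 2 | 182.6 − 84 = 98.6 |
| 4 | 1 (*k* = 2, *m* = 6) | 182.6 − 112 = 70.6 |

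These are possible combinations, not frequencies. Taking six months as 181 to 184 days moves the ends of the range to 69–72 and 153–156.

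**With delays.** Section 6.5.2.1 makes Day 42 of a cycle the point for discussing slow hematological recovery in Arm A with the sponsor, a delay of about 14 days. Section 6.5.2.2 sets the corresponding discussion point at four weeks. Section 5.3 stops treatment for APR-246-related toxicity of grade 3 or higher only when a dosing delay passes four weeks or the toxicity recurs after the maximum dose reduction. For *k* = 2 and *m* = 6 there are four intervals:
- 7 days late each time: 70.6 − 28 = 42.6 days of cover.
- 14 days late each time: 70.6 − 56 = 14.6 days.
- 28 days late each time: 70.6 − 112 = −41.4 days, so the last APR-246 dose falls about 41 days after required cover has ended.

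The break-even is 70.6 / 4 = 17.7 days of delay per interval. With three cycles of APR-246 alone, delays of 28 days each still leave 98.6 − 84 = 14.6 days. With delays of at most four weeks per interval, an uncovered dose therefore arises only on the longest route.

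**Sensitivity to wording.** If chemotherapy treatment is taken to end on day 28 of its last cycle, add 24 days throughout: 94.6 to 178.6 days on schedule. Four delays of 28 days then give 94.6 − 112 = −17.4, still negative. If an unscheduled early scan supported a switch after cycle 1, the on-schedule figure would be 182.6 − 140 = 42.6 days.

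**The case against.** The strongest reply is that no deficit has been shown. A patient on the full course has about 183 days after her last APR-246 dose only because chemotherapy ended on the same day. A reader might infer that six months is what APR-246 needs, and that the 28 to 112 days between the two stop dates are missing protection. The documents do not support that. Six months is attached to chemotherapy, and the visible text sets no contraception period for APR-246. Its toxicology is redacted, and the consent pages and Investigator's Brochure were not available. On schedule every APR-246 dosing day is covered, and the lowest figure exceeds the 30 days in 7.4.1, although that is a reporting window and not a contraception rule. All of this stands.

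A second reply is that the undefined phrase could be read to cover the whole course. Section 6.5.1.1 treats the four APR-246 days and the Day 4 chemotherapy as one cycle, and section 4.6 describes the course as cycles of the chemotherapy regimen with or without APR-246. That reading is possible, but 6.5.2 and 7.2.4 use the term for carboplatin and PLD. Two readings of a safety clause are themselves a reason to reword it.

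Third, the route is rare and controlled. The patient must be in Arm A, of childbearing potential, off both cytotoxics for adverse events, responding, and approved by the sponsor. The clause sets a minimum, so longer cover can be asked for when monotherapy is approved. This limits the size of the point, but nothing visible in the plan requires the longer cover.

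Two arguments should not be used against the plan. The early End of Treatment visit in 7.2.5 is timed "after the last administration of APR-246 if treatment is stopped early for any reasons", but Table 10 uses the same anchor for Arm B, which never receives that drug, so it is weak evidence of deliberate anchoring. Nor does the cisplatin substitution in 6.5.3 open a second gap: cisplatin replaces the combination chemotherapy and is already chemotherapy.

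**Conclusion.** The point holds as a minor wording defect that could be corrected (COULD). On the permitted APR-246-alone route, required contraception is tied to the last cytotoxic dose, which leaves about 71 to 155 days of minimum cover after the last APR-246 dose.

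That range assumes 28-day cycles without delay, a switch no earlier than after cycle 2, and chemotherapy ending on its last dosing day. The 71 days is not a floor: tolerated delays shorten it, and on the longest route an average delay above about 17.7 days per interval would leave the last APR-246 dose uncovered. Delays of that size at every interval are an extreme case, and the plan gives no estimate of how often they would occur.

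A reader might go further and infer that patients are being harmed or dosed without protection. The documents do not show that. Few patients, possibly none, would take this route, and what APR-246 itself requires cannot be judged from the visible text.

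**What to change.** In criterion 7 (synopsis and 5.1) and in 6.7, replace the timing phrase with: **during study treatment (including APR-246 given alone) and for at least six months after the last dose of any study treatment**. If the sponsor has data supporting a different period for APR-246, state that period separately, counted from the last APR-246 dose. Six months is offered here as a default that keeps one rule for all patients, not as a figure derived for APR-246.

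The cost is one phrase in three places, and in the consent form if it repeats the clause (not seen). For the few patients on this route it means about 28 to 112 more days of contraception, on schedule. Endpoints, sample size and analysis are unaffected.

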1.0 GENERAL INFORMATION

1.1 Protocol Number and Title of the Study

APR-407 PiSARRO: p53 Suppressor Activation in Recurrent High Grade Serous Ovarian Cancer, a Phase Ib/II Study of Systemic Carboplatin/Pegylated Liposomal Doxorubicin Combination Chemotherapy With or Without APR-246.

1.5 Independent Data Monitoring Committee (IDMC)

An Independent Data Monitoring Committee (IDMC) will review and evaluate safety data and reports on cumulated serious adverse events (SAEs). Based on this review the IDMC should provide

recommendations to the Sponsor regarding the ongoing scientific and ethical integrity of the study and in reference to the study protocol. The members of the IDMC serve in an individual capacity and provide their expertise and recommendations. The IDMC Charter will outline the roles and responsibilities and serve as the Standard Operating Procedure (SOP) for the IDMC.

The safety and well-being of the trial participants are the most important considerations and should prevail over the interests of the science and society.

2.0 INTRODUCTION AND RATIONALE FOR THE STUDY

2.1 Background Information

2.1.1 General Information

Aprea Therapeutics AB was founded in 2003 by the inventors, [name], [name], [name], [name], [name] and [name] together with Karolinska Innovations AB. The company is aiming to develop target specific drugs for the treatment of cancer by restoration of p53 function. Such treatment should induce massive apoptosis and thus eliminate the tumor.

The company has identified molecules that via p53-dependent pathways induce apoptosis in cancer cells with mutant or wild type p53. Aprea Therapeutics AB has since its inception confirmed the data in house and has screened for novel substances. The compound APR-246 has been selected as the company's first candidate drug (CD).

2.1.2 The p53 Protein and APR-246

P53 was discovered in 1979 as a cellular protein that forms a complex with the viral large T protein in SV40-infected cells. Later studies showed that p53 was a tumor suppressor which could inhibit cell growth and trigger cell death by apoptosis. TP53, the p53 gene is mutated in almost half of all human tumors. The p53 status of a tumor may have a strong impact on sensitivity to commonly used anti-cancer drugs and radiotherapy [1]. Thus, p53 is an important clinical marker and also a novel therapeutic target. In contrast to other tumor suppressor genes, TP53 is typically inactivated by single missense mutations, which is accompanied by loss of the remaining wild type allele. As a rule, mutant p53 proteins are deficient for specific DNA binding suggesting that DNA binding and transcriptional regulation of target genes are critical functions for p53-mediated tumor suppression [2].

The fact that TP53 is mutated in around 50% of human tumors, that mutant p53 protein usually accumulates at high levels, and that mutant p53-expressing tumors respond poorly to conventional therapy makes mutant p53 an attractive target for novel cancer therapy [3]. In hematological malignancies, between 5 and 20% of the patients carry a TP53 mutation in their malignant cell clone. However, for the current indication more than 95% of patients with High Grade Serous Epithelial Ovarian Cancer (HGSOC) carry TP53 mutations [4].

Recent studies have demonstrated that restoration of p53 in p53-deficient mouse tumors triggers rapid and efficient elimination of the tumor through cell cycle arrest, senescence and/or apoptosis [5]. This supports the idea that pharmacological reactivation of p53 should allow efficient elimination of tumors with minimal effects on normal cells.

The small molecule PRIMA-1 (later denoted APR-017) was identified in a cellular screen for compounds that preferentially induce apoptosis in human tumor cells expressing exogenous mutant p53. Optimization of APR-017 resulted in the structural analogue APR-246, the IMP for this study. Treatment with APR-246 has been shown to restore sequence specific DNA binding wild type

conformation and transcriptional transactivation to mutant p53 protein. Furthermore, APR-246 has been shown to synergize with the DNA damaging anti-cancer agents, including platinum compounds and doxorubicin (See IB).

2.2 Disease Background

Ovarian cancer is the seventh most commonly diagnosed cancer among women in the world, accounts for an estimated 239,000 new cases and 152,000 deaths worldwide annually [6]. Ovarian cancer has been of considerable interest to clinical cancer investigators due to the fact that it is among the most chemosensitive of all solid tumors [7]. It is frequently platinum sensitive initially and even in advanced disease the accepted management is a combination of surgery and platinum based chemotherapy.

Despite the evolution of surgical techniques and ever improving chemotherapy regimens, relapse and consequential disease progression remains the most challenging task. Screening has not yet proven an effective tool to diagnose patients at an earlier stage in their disease and late diagnosis is associated with relapse and death after repeated treatment cycles. The 5 year survival rate remains poor at less than 40% and this has remained unchanged for the last 20 years [6]. Thus, there is a need for improved treatment of relapsed ovarian cancer. The combination of carboplatin and pegylated liposomal doxorubicin is widely used in Europe following results of the multicenter phase III CALYPSO study which demonstrated non-inferiority of this combination over the standard carboplatin and paclitaxel combination arm in terms of PFS (11.3 months versus 9.4) with lower rates of severe and long-lasting side effects [8].

Despite rapid scientific advances in the last decades, it has proved difficult to improve outcomes beyond platinum-based therapy introduced in the late 1970s. Cisplatin, and subsequently carboplatin has been combined with other agents, especially taxanes to form the backbone of current treatment regimes. The combination is effective in first-line, platinum sensitive ovarian cancer, but unfortunately since most patients are diagnosed late, recurrence is common. Drug resistance does eventually develop due to repeated treatment with the same drugs. With each relapse, the response to treatment decreases with lower quality of life.

The median survival time for patients with advanced HGSOC is approximately 44 months. In platinum-sensitive cancer, tumor response to first line platinum-based treatment lasts at least 6 months following initial treatment. In the first line setting, carboplatin, generally in combination with a taxane provides impressive results with about a 70% response rate. Patients are retreated at relapse with platinum unless the cancer is platinum resistant (i.e. tumor progression within 6 months after completing first line treatment). Unfortunately almost 50% of Epithelial Ovarian Cancer (EOC) patients will relapse within 18 months and 75% by 30 months. The likelihood that a patient will respond to the reintroduction of a platinum-based regimen depends on the platinum-free interval (PFI), defined as the interval between the last dose of platinum and the time of relapse. Thus, fewer patients with a PFI of 6–12 months are expected to respond to the reintroduction of platinum-based chemotherapy, compared with patients with a PFI of 18–24 months.

As the majority of patients with advanced ovarian cancer will eventually relapse with incurable and terminal disease, there is significant unmet need for improved tools to aid earlier diagnosis and also

for establishing more effective alternative treatment options for the late stage resistant patient population. As such, there is a need for better first-line therapies that may delay or prevent relapse and improve survival rates. An unmet need also exists in the setting of recurrent disease, where currently used therapies have little impact on survival. As such the addition of a new drug on the market to current standard of care may impact significantly on patient management, given the current lack of effective treatment options once patients relapse.

High Grade Serous Ovarian Cancer (HGSOC) accounts for approximately 70% of malignant ovarian surface epithelial carcinoma in Europe and North America [9]. Mutant TP53 is a hallmark of HGSOC, resulting in deregulation of cell cycle checkpoints and uncontrolled tumor cell proliferation and thus represents a key driver event. Pathogenic TP53 mutations have been quoted as occurring in up to 96% of patients with HGSOC [4]. Rearrangements in TP53 have been shown to correlate significantly with resistance to chemotherapy, early relapse and shortened overall survival.

Almost 90% of HGSOC initially present as advanced-stage (stage III or IV) disease [10] thus spreading outside the pelvic cavity hence accounting for low median survival times. There is a need for improved treatment of HGSOC since present therapies have little impact on survival. APR-246 may offer such an opportunity since it has been shown to induce apoptosis and cell death in cancer cells with mutant or otherwise non-functional p53, and in addition to display strong synergistic anticancer effects in combination with several conventional chemotherapeutic drugs including platinum drugs and doxorubicin.

